3.1 General Design

[figure not shown]
This is a randomized, placebo-controlled 2-arm trial that will compare placebo with ISD/HY combination therapy. Participants will be randomized in a 1:1 fashion to ISD/HY or placebo. As shown in Figure 4, the study will be conducted in 2 phases: a 4-week dose escalation phase and a 22-week treatment phase.

All randomized participants will initiate treatment with therapy three times daily. The active therapy group will receive a one-week supply of ISD/HY 10/10 followed by a one-week supply of ISD/HY 20/35 3x/day. The placebo control group will receive an identical supply of placebo and will follow the same

schedule as the active therapy group. At the 1 week and the 2 week visits, tolerability and hypotension will be assessed. If the starting dose and first dose titration is tolerated, participants will be increased to ISD/HY 40/75 mg 3x/day (active therapy) or placebo and they will receive an additional 2 weeks drug supply. Tolerability will be re-evaluated after an additional 2 weeks and at 4 week intervals thereafter. At 4 weeks, participants tolerating the full dose will receive a 12-week supply of study medication at the appropriate dose. At 16 weeks, an additional 10-week supply will be provided. Participants not tolerating the full dose at this point may reduce to the starting doses of active therapy at this visit. In the event of poor tolerance or drug related adverse events (e.g. hypotension, intra-dialytic cramping), the dose of study medication may be held or reduced to a minimum dose of ISD/HY 10/10 mg 3x/day (active therapy) or matched placebo 3x/day. Except where un-blinding is necessary for safety purposes, participants not tolerating the lowest dose of active therapy will be reduced to double placebo therapy in order to maintain unbiased assessments of study endpoints.

In order to maintain the blind, all study participants, regardless of randomized assignment, will receive new dosing kits within 1 day (with a window of up to 3 days) of the 1, 2, 4, and 16 week visits, and will be evaluated bi-weekly during the dose escalation phase.

Figure 4. Study Design

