3.2 Study Endpoints

3.2.1 Safety Endpoints

The safety endpoints are:

- 1) Adverse events
- 2) Adverse events that preclude further treatment with the study agent
- 3) Serious hypotension defined as hypotension requiring hospitalization or treatment in an emergency room and not attributable to overt sepsis, acute myocardial infarction, or other cardiovascular event (e.g. aortic dissection)
- 4) Recurrent intra-dialytic hypotension is defined as systolic blood pressure <80 mm Hg during ≥3 dialysis sessions per rolling 30-day period or treatment for either hypotension or symptoms of hypotension if systolic blood pressure is <100 mm Hg during ≥3 dialysis sessions per rolling 30-day period. Treatment includes saline infusion, lowering of the ultrafiltration rate or other

interventions directed at hypotension such as vasopressor agents. Symptoms include but are not limited to muscle cramping, lightheadedness, and nausea.

- 5) Inter-dialytic hypotension defined as systolic blood pressure <90 mm Hg or hypotension requiring adjustment in blood pressure medications or treatment in an emergency or hospitalized setting.
- 6) Mean pre-dialysis blood pressure
- 7) Mean lowest intra-dialytic blood pressure
- 8) Cardiovascular hospitalization
- 9) Stroke
- 10) Death

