5.2 Treatment Regimen

As depicted in Figure 4, 16 participants will be randomized in a 1:1 fashion to either placebo 3x daily or ISD/HY 10 mg/10 mg, 3x daily for 1 week. Doses scheduled to be administered within 2 hours prior to a dialysis session will be held and administered post-dialysis on dialysis days. Participants will be contacted by phone or in person to review tolerability and adverse events at 1 week after drug initiation and will be examined in person at 2 weeks. Dialysis records will be reviewed for hypotension at each visit. The sequence will be repeated following the scheduled dose titration which will occur following the 2-week visit. Adjustment to dosage of concomitant medications, the dialysis prescription, or the study drug on the basis of hypotension will occur as described in Section 6.7.

All randomized participants will receive an initial one-week supply of study medication following the baseline visit, and a one-week supply after the Week 1 visit. Those assigned to ISD/HY will begin treatment at 10/10 mg 3X daily. Participants randomized to placebo will follow the identical schedule. Participants will be contacted at 1 week to check for the occurrence of adverse events and dose-limiting symptoms, and those tolerating the study drug will have the dose increased to ISD/HY 20/35 mg 3X daily or placebo. At Week 2 participants will be examined in-person at their dialysis units. Adverse events will be reviewed and dialysis run sheets will be examined for the occurrence of inter- or intra-dialytic hypotension at each visit. In the absence of dose-limiting hypotension or other adverse events, the dose of ISD/HY will be increased to 40/75 mg 3X/daily following the Week 2 visit.

During the 4-week dose escalation phase, a study drug request form will be entered into the data management system at 1 week, 2 weeks and 4 weeks to request the next supply of study drug. Unless there is a contraindication to a dose increase (e.g. hypotension), the investigator will indicate approval for dose escalation on the request form. The Data Management System will generate a unique kit number based on the randomized treatment assignment and the prior dose. If up-titration to the next dose is contraindicated, the Clinical Center investigator will indicate this on the study drug request form and a kit number corresponding to the current dose of will be generated.

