If down-titration of the study drug dose is required during the dose escalation phase or during the treatment phase, the Clinical Center investigator will request a dose reduction on the study drug request form. In this case, a supply of blinded study medication using the next lower dose of ISD/HY or placebo will be provided. In the event that a participant is already receiving the lowest dose, study medication will be discontinued. In the event that a 3rd down titration of dose is required study medications will also be discontinued. Un-blinding to preserve patient safety will be considered via a formal request to the DCC.

If the dose escalation schedule is interrupted (e.g., if a participant is hospitalized at the scheduled time of dose escalation and did not take study drug during the hospitalization), dose escalation will be delayed until the participant has had access to the current dose of study drug for the specified interval (1 week for the first dose level, 2 weeks for the second dose interval). If, due to a considerable delay in dose escalation, a participant has not reached the final dose assignment by their Week 8 visit, the participant will remain at the current dose of study drug for the remainder of the study and the treatment phase will be shortened accordingly such that the total duration of study participation is not increased as a result of the delay. For example, if dose escalation is not completed until week 10, the treatment phase will be 16 weeks rather than 22 weeks.

Participants will be contacted by phone or in person at Weeks 1 and 3 (plus or minus 3-5 days) as described above and will be examined in-person at Weeks 2 and 4. Dialysis records will be reviewed at each time point. Following the Week 4 visit a 12-week supply of the maximal tolerated dose of study medication will be distributed to participants who will be evaluated in-person at the dialysis unit every 4 weeks for the duration of the study. A 10-week supply of study medication will be distributed to participants following the Week 16 visit. At Week 26, participants will have a close-out visit, echocardiography and PET scan at the medical center and will then discontinue study medications.

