- As-treated population: The as-treated population is the same as the ITT population (i.e., any participant randomized into the study regardless of whether study drug was received). However, for the as-treated analysis, patients in the active drug group who did not receive at least one dose of study drug will be classified into the placebo arm.
- All-treated population: Any participant randomized into the study who received at least one dose of study drug.
- Per-protocol population: Any participant who was appropriately randomized, and received the protocol-dictated study drug exposure ($\geq 75\%$ of prescribed doses) and endpoint assessments through 24 ± 2 weeks.

Because dose-related efficacy and safety are important questions of interest in this study, the ITT analysis will be supplemented with an analysis of the as-treated population. Although ITT approaches provide the least-biased analysis of treatment efficacy and safety, as-treated analyses provide important complementary information on biological effectiveness of therapy (e.g. theoretical efficacy if drug were tolerated by all participants) and on the effects of actual doses used that is not captured by (ITT) analyses in which the unit of analysis is a randomized therapy that may not have been used by individual participants¹⁴⁹. For this reason, as-treated approaches provide important complementary information to ITT analyses and are typically mandated as an important secondary analyses of clinical trials by the FDA¹⁴⁹. Given a treatment protocol that allows for dose reduction of study medications, the as-treated analysis will provide critical information in this trial for assessing dose-related efficacy and the incidence of adverse events such as hypotension. As-treated analyses will assign treatment dose according to the dose used at the time of an adverse event (safety analyses) or according to the mean dose received during the trial (efficacy analysis).

In general, missing data will not be imputed. Every effort will be made to use statistical methods that are robust to missingness, and the number of participants included with each analysis will be given with the results.

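### The as-treated dose analysis credits a hypotension event that builds up over as long as 30 days to a single dose, although the two lower doses last one week each, so its dose-specific rates are biased in a direction the plan leaves open

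*Combined protocol and SAP*

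**What the plan says.** Section 3.2.1, item 4: "Recurrent intra-dialytic hypotension is defined as systolic blood pressure <80 mm Hg during ≥3 dialysis sessions per rolling 30-day period". A second route to the same event is treated hypotension or symptoms with systolic pressure below 100 mm Hg, over the same number of sessions and the same 30 days. No start for the window is given.

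Section 3.1 plans "a one-week supply of ISD/HY 10/10 followed by a one-week supply of ISD/HY 20/35 3x/day", then 40/75 mg, within "a 4-week dose escalation phase and a 22-week treatment phase". That leaves 24 of the 26 weeks at 40/75 for a participant who titrates on schedule. Placebo follows the same calendar (section 5.2).

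Section 7.3 sets the attribution rule for the as-treated population: "As-treated analyses will assign treatment dose according to the dose used at the time of an adverse event (safety analyses". It says that this analysis "will provide critical information in this trial for assessing dose-related efficacy and the incidence of adverse events such as hypotension".

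Section 7.4.1 models safety events by logistic or Poisson regression on assigned treatment and the stratification variable, and repeats this by analogy in the as-treated population. It states no period term, no exposure offset and no rule for a window that spans two doses.

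**The concern.** An event that needs three sessions cannot occur until the third session after the window opens, and the chance of meeting it keeps rising until 30 days of sessions have accrued. Each lower-dose step ends long before that. The rule then credits the whole event to the dose in use when the third session occurs, even if earlier sessions were at a lower dose or before treatment. Dividing by person-time at each dose does not cure this, because the event rate per week itself depends on how full the window is.

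At stake are the dose-specific estimates of intra-dialytic hypotension that would be carried into a later trial. Section 7.4 says that point estimates and confidence intervals for planning are the main product of this pilot, so bias in an estimate matters even where no test is significant.

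**Working it through.** **The plan's own figure.** The plan gives no event rate by dose. Its nearest safety figure is Table 2, the chance of at least one event among 8 participants, 1 − (1 − rate)^8. At 0.10 this is 1 − 0.9^8 = 0.570, and at 0.20 it is 1 − 0.8^8 = 0.832. Both match the plan (0.57 and 0.83) and are not in dispute.

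**Inputs from the documents.** At least 3 sessions in 30 days (3.2.1); one week at each lower dose and 24 weeks at 40/75 (3.1, 5.2); dose taken at the time of the event (7.3).

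**Assumptions not in the documents.** Three sessions a week; per-session probability p, the same at every dose (no drug effect). Risk is either equal across patients or varies between them (beta distribution, parameters summing to 5). In the look-back runs, screening falls 14 days before first dose and the section 4.2(d) exclusion is applied.

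**Step 1: exact binomial, window opening at first dose.** Sessions available are 3 by the end of week 1, 6 by the end of week 2, and 3 × 30/7 ≈ 13 in a full window. At p = 0.10:
- week 1: 0.1^3 = 0.001
- by the end of week 2: 1 − 0.9^6 − 6(0.1)(0.9^5) − 15(0.1^2)(0.9^4) = 1 − 0.5314 − 0.3543 − 0.0984 = 0.0159
- full window of 13 sessions: 0.134

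At p = 0.05 the three values are 0.0001, 0.002 and 0.025; at p = 0.20 they are 0.008, 0.099 and 0.498.

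**Step 2: simulated first events per 100 person-weeks, planned calendar, no drug effect.** The last digit moves a little between runs.

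| Window | Risk | 10/10 | 20/35 | 40/75 |
|---|---|---|---|---|
| From first dose | equal, p = 0.05 | 0.02 | 0.20 | 1.24 |
| From first dose | equal, p = 0.10 | 0.10 | 1.54 | 6.04 |
| From first dose | varying, mean 0.10 | 0.85 | 5.49 | 2.35 |
| Looks back | equal, p = 0.03 | 0.42 | 0.39 | 0.36 |
| Looks back | equal, p = 0.10 | 8.70 | 7.55 | 6.14 |
| Looks back | varying, mean 0.10 | 6.24 | 4.22 | 1.31 |

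The true dose effect is nil in every row, yet the pattern rises, peaks in the middle, is nearly flat, or falls.

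**Step 3: dose reduction after events.** With repeat events counted, the window from first dose, varying risk and mean p = 0.08, the rates are 0.57, 3.88 and 5.61 without reduction. They are 8.95, 7.47 and 1.70 if the dose drops after every event, because susceptible patients move to the lower doses.

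**Step 4: misattribution.** With equal risk and the window from first dose, about 90% of first events in weeks 3–4, all credited to 40/75, include at least one lower-dose session. Over all first events credited to 40/75 the share is 11%, 19% and 49% at p = 0.05, 0.10 and 0.20.

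**Step 5: the alternatives.** Qualifying sessions divided by sessions at each dose has expected value p at every dose on the planned calendar (0.10, 0.10, 0.10 at p = 0.10). Active against placebo in the same weeks has expected ratio 1.0, because both arms share the window and the schedule.

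**The case against.** A reader might infer that the analysis must show hypotension climbing steeply with dose. The documents do not support that. They do not say that the window opens at first dose, and look-back is feasible: section 4.2(d) applies a similar 30-day rule before screening, and dialysis records are reviewed at screening and baseline (section 15). Sections 5.2 and 6.7 allow dose reduction, and this very event triggers the section 6.7 procedures, so lower-dose time is not confined to weeks 1 and 2. Under constant risk the build-up ends after about 30 days (at p = 0.10 the rate is 5.54 on days 15–30 and 6.14 afterwards). All of this stands, and it makes the direction unknown. It does not make the estimates unbiased.

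A reader might also infer that less frequent contact after week 4 distorts detection. Section 6.4 and the visit schedule have dialysis records reviewed at those later contacts too, so that argument fails. If it held, it would lower counts at 40/75.

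The as-treated analysis is secondary, section 7.3 labels it exploratory, and section 7.4 lets methods be revised. With 8 active participants a false significant result is unlikely if person-time is used. With the window from first dose, varying risk and no dose reduction, it arises in 0 to 1.6% of simulated trials for mean p from 0.03 to 0.20. If exposure time is ignored and the proportions are compared by Fisher's exact test, the figure is 0%, 1%, 14% and 53% at 0.03, 0.05, 0.10 and 0.20. The exploratory label answers false-positive tests. It does not answer a biased estimate in an analysis that the plan itself treats as critical for hypotension.

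Finally, the larger values of p are hard to square with the eligibility rules: at p = 0.20 about half of candidates would have three qualifying sessions in 13 (0.498). At p = 0.05 about 26% would have the event by week 26, or about 2 of 8 active participants.

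**Conclusion.** The concern holds for one endpoint in one secondary analysis. The attribution rule in section 7.3 gives dose-specific rates of recurrent intra-dialytic hypotension that are not comparable across doses even with no drug effect. With the window from first dose and constant risk, the false rise at p = 0.10 is about 60-fold from 10/10 to 40/75 (6.04/0.10) and about 4-fold from 20/35 (6.04/1.54). With look-back, varying risk or event-driven dose reduction, the pattern may be nearly flat, non-monotone or reversed. Choosing among these rules after unblinding could settle the apparent answer.

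The sizes rest on the assumed session frequency and p; the mechanism does not. The between-arm ITT comparison is unaffected because placebo shares the calendar. Serious hypotension, inter-dialytic hypotension, mean pre-dialysis pressure and mean lowest intra-dialytic pressure have no 30-day window and do not have this artefact.

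**What to change.** In section 7.3, for dose-level comparisons of intra-dialytic hypotension:
- Replace the 30-day event with qualifying sessions per dialysis session, each session classed by the dose in use at that session.
- Alongside it, show active versus placebo within the same nominal period (weeks 0–1, 1–2, 2–4 and 4–26).
- Keep the 30-day endpoint for the between-arm ITT comparison, and state when its window opens and how repeat events count.

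The period limits depend on the length of the second dose step. Section 5.2, on interrupted escalation, gives "1 week for the first dose level, 2 weeks for the second dose interval", while section 3.1 and the rest of 5.2 plan one week. These passages must be reconciled.

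The cost is SAP wording and a little programming, since run-sheet blood pressures are already collected (section 15, footnote 2). Two limits remain and should be stated. The per-session rate by actual dose is still confounded once doses are reduced because of events. The period comparison reflects the nominal step, not the dose received. With 8 against 8, both stay descriptive.

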7.4 Statistical Methods

In addition to the analyses described subsequently, descriptive statistics will be used during the course of the project as part of data management procedures for monitoring data quality. A brief overview of some of the statistical methods that may be used at the time of analysis, both for descriptive purposes and in more comprehensive analysis of the primary research questions, is summarized in the following

sections. It is recognized that these methods may be revised and additional ones considered as the details of the specific analyses are developed.

Given the pilot nature of this study, the primary objectives of this study are to derive pilot estimates of efficacy and safety. As noted above, given the small sample size, the power to detect small to medium effect sizes or adverse event rates will be limited. However, the point estimates and confidence intervals around effect sizes and adverse event rates are expected to provide information needed for the planning of future studies.

7.4.1 Descriptive Analysis

Standard descriptive statistics will be used to summarize baseline characteristics and study outcome measures at each follow-up visit, both overall and within each treatment group. Examination of baseline characteristics will include estimates of the distribution of age, race, and other demographic characteristics, lab measures and study center. Summary statistics such as means, medians, and ranges will be produced for all measured variables. Frequencies will be computed for all categorical and ordinal variables. Graphical methods including stem-and-leaf diagrams and boxplots will be used to examine distributions, identify potential influential points, and guide in the choice of transformations, if warranted. The balance of baseline measures across the treatment groups will be compared using appropriate k-sample tests, including X-Squared tests and Fisher's exact tests.

Analysis of Primary Efficacy and Safety Outcomes Mean \pm standard deviation or median (interquartile values) of baseline and end of study measurement in the primary endpoint E' will be presented. Change in E' velocity or CFR at 26 weeks will be assessed and reported quantitatively, and descriptive statistics for absolute and % change will be provided. Mixed effects linear regression models with baseline covariate adjustments will be used for assessment of treatment effects. Model assumptions regarding homoscedasticity and normality will be examined using standard techniques.

For the safety endpoints, tables with percent incidence and incidence rate (for events that can occur more than once during follow-up) will be prepared. Differences in incidence and incidence-rate will be assessed using logistic regression or Poisson regression with factors for assigned treatment and the stratification variable. In particular, for safety endpoints, we will investigate the potential shift in blood pressure in control and treatment groups with monthly measure of blood pressure. We will use mixed effects linear regression models to assess the direction and time averaged magnitude of change in potassium, with and without controlling for baseline covariates. The proportion of serious hypotension in treatment and control groups will be compared with Chi-square test or Fisher's exact test.

The primary analysis will examine the intention to treat population. Exploratory analyses will be repeated in the as-treated, all-treated and per-protocol populations (see **Section 7.3**) using analogous techniques. $P<0.05$ will be considered significant in all analyses.

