LVEF	left ventricular ejection fraction
LVMI	left ventricular mass index
mEq	milliequivalent
MM	millimeter
MG	milligram
MOP	manual of procedures
MRI	magnetic resonance imaging
MI	myocardial infarction
NIDDK	National Institute of Diabetes and Digestive and Kidney Diseases
NO	nitric oxide
NOS	nitric oxide synthase
OHRP	Office of Human Research Protections
PET	positron emission tomography
PHI	protected health information
PICP	procollagen type I carboxy-terminal peptide
PTH	parathyroid hormone

QD	daily
RCT	randomized controlled trial
SAE	serious adverse event
SAP	statistical analysis plan
SBP	systolic blood pressure
TDI	tissue Doppler index
TSP	thrombospondin II
UAE	unanticipated adverse event
VEGF	vascular endothelial growth factor

Study Summary

Title	Safety and Cardiovascular Efficacy of Hydralazine and Isosorbide Dinitrate in Dialysis-Dependent ESRD
Short Title	HIDE Study
Protocol Number	2014P001544/BWH
Phase	Pilot
Methodology	Randomized, double-blind, 2-arm
Study Duration	2 years
Study Center(s)	Brigham and Women's Hospital
Objectives	
• To generate pilot data on the safety and tolerability of hydralazine (HY) isosorbide dinitrate (ISD) combination therapy in patients with dialysis-dependent ESRD.• To generate pilot estimates of the effect of HY/ISD combination therapy compared with placebo on cardiovascular efficacy parameters in patients with dialysis-dependent ESRD.
Number of Participants	16
Diagnosis and Main Inclusion Criteria	Dialysis-dependent end-stage renal disease
Study Product, Dose, Route, Regimen	ISD/HY 10 mg/10 mg, 3X/day for 1 week, orally ISD/HY 20 mg/35 mg, 3X/day for 1 week, orally ISD/HY 40 mg/75 mg, 3X/day for 2 weeks, orally
Duration of administration	26 weeks
Major Outcomes	
• Safety: hypotension, intra-dialytic cramping• Tolerability: treatment adherence• Efficacy: a) change in mitral annular E' velocity; b) change in CFR• Feasibility: recruitment rate, retention, dosing completeness
Statistical Methodology	Mixed effects linear regression models will be used to assess the direction and time averaged magnitude of change in E' and CFR efficacy parameters, with and without controlling for baseline covariates, to compare the effects of therapy. The incidence of safety events, especially hypotension, in treatment and placebo groups will be compared with Chi-square test or Fisher's exact test.

1 Introduction

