7.1 Sample Size Determination

Sample size considerations were framed using standard study design parameters to ensure 80% power to detect pre-specified effect sizes utilizing intermediate outcomes. However, for this early phase pilot study, the primary focus is directed at providing pilot efficacy, safety and feasibility information, with no attempt to create critical test result regions for standard hypothesis testing. Results will nevertheless provide preliminary estimates needed to guide design of subsequent, more robust studies and will provide information on safety and tolerability events occurring at high event rates which can be incorporated into the design of further studies.

With 8 participants per group, there will be 80% power to detect a change in CFR of 0.75 (unitless measure), assuming a common standard deviation for change in CFR of 0.5¹³⁸⁻¹⁴³. Assuming the common SD of E' is 2.0 cm/s and baseline is 5.8 ± 1.8 cm/s^{39, 144-146}, we will be able to detect a difference of 3.0 cm/s with 80% power. Changes of this magnitude have been observed in other settings^{144, 147, 148}. Baseline variables will be presented using standard descriptive statistics according to distribution. P<0.05 will be considered significant without correction for multiple comparisons given the pilot nature of this proposal.

Although the detectable change in each effect measure is large, detectable differences are, as noted above, clinically relevant. Further, given the pilot nature of this study, additional trials will be required regardless of whether a significant difference in the efficacy measures is detected. Point estimates and standard deviations around these measures will provide the needed estimates of expected change so that more robust studies can be designed.

It is similarly noted that under the proposed sample size, estimates of safety and tolerability event rates will provide relatively crude estimates of the true event rates. Confidence intervals around estimated event rates based on various observed event rates within the treatment (or control arm) will be large and are provided below for a range of detected event rates (Table 1). As shown in Table 2, power to detect event rates $\geq 20\%$ will be good while power to detect lower event rates within each study arm will be limited for events with a true rate <15%.

Table 1. Confidence interval for estimated event rates within each study arm

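### Between-arm safety comparisons rely on ordinary logistic and Poisson regression, which with 8 per arm will often give no finite odds ratio and, for recurrent events, make no allowance for differences between participants

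*Combined protocol and SAP*

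**What the plan says.** Three statements cover the between-arm safety comparison.

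- Section 7.4.1 gives the regression: "Differences in incidence and incidence-rate will be assessed using logistic regression or Poisson regression with factors for assigned treatment and the stratification variable". The stratification variable is LVEF at or below 45% versus above.
- The same section adds, for one endpoint: "The proportion of serious hypotension in treatment and control groups will be compared with Chi-square test or Fisher's exact test".
- The Study Summary applies that pair of tests more widely: "The incidence of safety events, especially hypotension, in treatment and placebo groups will be compared with Chi-square test or Fisher's exact test".

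For repeatable events, section 7.4.1 says that "tables with percent incidence and incidence rate (for events that can occur more than once during follow-up) will be prepared". It names Poisson regression for the rates and mentions no dispersion term, robust variance or person-time offset. No small-sample method is named for the LVEF-adjusted comparison, and there is no fallback if a model has no finite estimate.

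On the weight these analyses carry, section 7.1 frames the pilot "with no attempt to create critical test result regions for standard hypothesis testing", and section 7.4 says that "these methods may be revised and additional ones considered as the details of the specific analyses are developed". Yet section 7.1 also says that P<0.05 "will be considered significant without correction for multiple comparisons given the pilot nature of this proposal", and the end of section 7.4.1 applies the same threshold to all analyses.

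**The concern.** Safety is a primary objective (section 2.1) and there are 16 participants. Maximum-likelihood logistic regression has no finite treatment odds ratio when one arm has no events, and at this size an empty arm is common at the event rates the plan itself considers. Poisson regression treats a participant's repeated events as if all participants in an arm and stratum shared one underlying rate. If some are much more prone to events than others, its standard errors are too small and its p-values too low. Chi-square is offered at a size where its usual condition cannot hold.

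At stake is whether the between-arm safety contrast can be reported at all, and whether a rate difference declared at P<0.05 can be trusted. Section 7.4 expects that "point estimates and confidence intervals around effect sizes and adverse event rates are expected to provide information needed" for planning later trials.

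**Working it through.** **1. The plan's own figure.** Table 2 (section 7.1) gives the chance of at least one event in an arm of 8, which is 1 − (1 − p)^8. This yields 0.337, 0.570, 0.728, 0.832, 0.900 and 0.942 for p = 0.05 to 0.30, against the printed 0.34, 0.57, 0.73, 0.83, 0.90 and 0.94. It reproduces. An arm is therefore empty with probability 0.95^8 = 0.663 at 5% and 0.90^8 = 0.430 at 10%.

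**2. At least one empty arm.** The probability is 1 − [1 − (1 − p1)^8][1 − (1 − p2)^8]. The rates are taken from Table 2's range; the pairings are assumed, because the plan gives no between-arm difference.

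- 5 vs 25%: 1 − 0.3366 × 0.8999 = 0.697
- 10 vs 30%: 1 − 0.5695 × 0.9424 = 0.463
- 20 vs 30%: 1 − 0.8322 × 0.9424 = 0.216

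With the LVEF factor in the model, checking every table for separation with 0 to 4 low-LVEF participants per arm (assumed), the treatment odds ratio is not finite in 70–71%, 46–48% and 22–23%. These are chances of a degenerate estimate, not of a wrong conclusion.

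**3. Chi-square.** With s events in total and 8 per arm, the smallest expected count is min(s/2, (16 − s)/2), which is at most 4. The usual minimum of 5 is never met. Over all 81 possible tables, two-sided at 0.05:

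| | Fisher | Uncorrected chi-square | Yates chi-square |
|---|---|---|---|
| Maximum size | 2.1% | 7.7% | 2.1% |
| Tables on the other side of 0.05 from Fisher | – | 10 | 0 |
| Probability of disagreement (5 vs 25 / 10 vs 30 / 20 vs 30%) | – | 6.4 / 7.8 / 4.6% | 0 |

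Example, 4/8 vs 0/8. Uncorrected chi-square is 16 × 32² / (8 × 8 × 4 × 12) = 5.33, p = 0.021. With Yates' correction it is 16 × 24² / 3072 = 3.00, p = 0.083. Fisher's p is 2 × 70/1820 = 0.077.

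**4. Poisson for recurrent events.** The documents give neither a mean count nor a between-participant spread, so both are assumed. With arm totals A and B and equal person-time (assumed), the Wald statistic is ln(A/B)/√(1/A + 1/B). With equal numbers per stratum, the stratum factor changes neither the estimate nor its standard error. Gamma-Poisson simulation with 200,000 runs per cell, both arms having the same true rate, gives this type I error:

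| Mean events | CV 0 | CV 0.5 | CV 1.0 |
|---|---|---|---|
| 0.25 | 0.001 | 0.001 | 0.003 |
| 0.5 | 0.011 | 0.016 | 0.034 |
| 1 | 0.036 | 0.059 | 0.128 |
| 2 | 0.045 | 0.100 | 0.242 |
| 5 | 0.047 | 0.186 | 0.413 |

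A rough check: heterogeneity multiplies the variance of a count by 1 + mean × CV². At mean 5 and CV 1 that factor is 6, and 1.96/√6 = 0.80 corresponds to a two-sided error of about 0.42. At means of 0.25 to 0.5 the difficulty is instead an empty arm with no finite rate ratio, in 4% to 31% of trials.

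**The case against.** The strongest reply is that the plan already contains what is needed. Fisher's test is named and is valid with an empty arm. Chi-square or Fisher is common shorthand for using Fisher when counts are small, and here that convention always selects Fisher. Section 7.4 leaves the methods open to revision, and omitting a dispersion term from an overview is ordinary. Much of this stands. The missing rule between the two tests would, alone, be only a missing detail. What remains is that Fisher's test as named is an unadjusted 2×2 comparison, while the stated methods for the LVEF-adjusted and recurrent-event comparisons are the plain models.

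Three stronger readings are tempting and are not supported.

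- A reader might infer that an infinite odds ratio defeats the pilot's purpose. Section 7.4 speaks of intervals around effect sizes and adverse event rates. It does not promise a safety odds ratio, and Table 1's per-arm intervals survive an empty arm.
- A reader might infer that the choice between chi-square and Fisher will swing conclusions. That holds only for the uncorrected statistic. The plan does not say which version is meant, and with Yates' correction no table is discordant.
- A reader might infer that the Poisson analysis will be badly anticonservative. The documents do not settle it. Section 8.3.2 describes frequent hypotensive events in hemodialysis patients generally, but section 4.2 excludes those with recurrent intra-dialytic hypotension. At low means there is no inflation.

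**Conclusion.** The point holds as an inexpensive improvement to consider, not as a flaw that invalidates the safety analysis. The firm part is arithmetic: with 8 per arm, the logistic model in section 7.4.1 has no reportable treatment odds ratio or Wald interval in roughly 70%, 46% and 22% of trials in the three scenarios. This depends only on the arm size and the assumed pairs of rates; the LVEF split hardly matters.

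The Poisson part is conditional. Type I error of about 6% to 41% requires a mean of 1 to 5 events and a between-participant CV of 0.5 to 1.0, neither of which is in the documents. Without heterogeneity, or at means of 0.5 or less, it stays below 5%.

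The chi-square part is minor: up to 7.7% size and 4.6% to 7.8% disagreement with Fisher's for the uncorrected version, and none with Yates' correction. All calculations assume two-sided tests and 8 evaluable participants per arm.

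**What to change.** In the Study Summary and section 7.4.1, delete chi-square and name one method for each type of comparison.

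- **Binary, unadjusted (main result):** the between-arm risk difference with an exact unconditional 95% confidence interval, and Fisher's exact test for the p-value.
- **Binary, LVEF-adjusted (supportive):** Firth-penalised logistic regression with profile-likelihood intervals.
- **Recurrent events:** rates with a person-time offset and quasi-Poisson inference. If an arm has no events, use a permutation test of participant-level rates within LVEF strata, and report the per-arm rates because no ratio is estimable.

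Fisher's is sufficient and is the smaller edit. Its one awkwardness is that it contradicts the Chan-Zhang exact interval for 4/8 vs 0/8 (p = 0.077; risk difference 0.50, interval 0.06 to 0.84), for 8/8 vs 4/8 and for their arm-swapped versions. Those tables arise in 5.7%, 5.9% and 2.5% of trials in the three scenarios. Boschloo's test avoids this and is optional.

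The cost is wording and standard software, with no change in sample size. No choice brings useful power: at 10 vs 30% it is about 3% for Fisher's and 8.8% for Boschloo's, so the interval should lead. Firth estimates are finite but very wide. For 5/8 vs 0/8 with two low-LVEF participants per arm, the odds ratio is 23 (95% CI 1.9 to 3,407) if one of the five events is in the low-LVEF stratum, 46 (2.8 to 7,596) if none is, and about 28 (2.1 to roughly 5,550) if two are. The permutation fallback gives a p-value but no rate ratio.
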